- 2) the postpartum face-to-face meeting takes place at the routine 6 wk postpartum visit and adherence is facilitated by bus passes, cafeteria vouchers, and the 2006 Mass insurance reform law providing free health care insurance for residents earning <150% of the federal poverty level. However, if a woman does not intend to attend this visit, the health educator will meet the women at locations outside the hospital, with consideration for the participant's and the health educator or assessors level of comfort (i.e., their pediatrician's office, their home, a community center). Locations will be selected for privacy (for example, an unused exam room at a pediatrician's office) and only staff who have experience making home visits will be permitted to complete home visits.
- 3) The 6 mos and 1 yr postpartum assessments will be conducted in the hospital or at a location outside the hospital with consideration for the participant's and the health educator or assessors level of comfort
- 4) Approximately 5% of participants in our prior pregnancy cohorts left the Springfield area after delivery; however, travel funds are budgeted for assessors to travel to the broader tri-state area (MA, NY, CT) if necessary.
- 5) Delivering the intervention does not rely upon women remaining in the immediate area during the postpartum year as it is based upon tested mailed print-based materials and telephone contacts. In addition to providing home/cell/work numbers, women will be asked to provide the contact information for a person close to them. Pre-paid cell phone time will be provided as an additional incentive.

D.5. Randomization

Immediately prior to randomization (~12 weeks GA), participants will be evaluated for study inclusion by answering if their provider has restricted their physical activity during this pregnancy. If they answer yes, their medical records will be reviewed by [name] (Co-Investigator, and Director of Maternal/Fetal Medicine at Baystate). Eligible patients will be randomized into either the Lifestyle Intervention vs. the Health and Wellness Comparison Group. Randomization will be stratified based on age (<30, >30 years) and pre-pregnancy BMI (overweight >25-<30 kg/m² vs. obese >30 kg/m²). Within each strata, a blocked randomization will be used such that both treatment groups will be assigned an equal number of times in each set of 4 sequentially enrolled patients.

D.6. Intervention

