We will consider the following factors as covariates: Social Support for diet and exercise will be measured via the Social Support for Exercise (SSE). The SSE has three subscales (Family, Friends, Rewards/Punishments) and acceptable internal consistency (alphas .61-.91) and criterion validity.¹ Clinical Characteristics of the Current Pregnancy: will be abstracted from the medical record utilizing customized software developed in our previous studies. Variables include: degree of abnormality on glucose tolerance testing during pregnancy defined as: 1) normal results on the screening 50-g OGTT; 2) failed screening test with normal results on the diagnostic 100-g test; 3) impaired glucose tolerance (IGT) defined as failed screening test and exceeded <1 cutpoints on the 100-g test; and 4) GDM defined as failed 50-g test and exceeded 2 or more cutpoints on the 100-g test;¹⁶³ treatment for abnormal glucose tolerance during pregnancy (e.g., diet, oral hypoglycemic and/or insulin); other pregnancy complications (e.g., hypertensive disorders, preterm birth, infection, cesarean delivery, NICU admission, Apgar score). Medical History: will include: personal history of GDM, family history of diabetes, previous infant with anomalies, still birth, or macrosomia, infertility, and parity. Sociodemographic Factors: will include income, level of education, and health insurance; acculturation via the Psychological Acculturation Scale,¹⁶⁴ language preference, and generation in the U.S. Smoking and Substance Use: Alcohol consumption, smoking, and drug use will be collected via questions from the Pregnancy Assessment Monitoring System.¹⁶⁵ Sleep: Pregnancy and postpartum sleep will be collected via The Pittsburgh Sleep Quality Index (PSQI).¹⁶⁶ Depression: Pregnancy and postpartum depression will be assessed via the Edinburgh Postpartum Depression Scale¹⁶⁷ validated in Hispanics.¹⁶⁸ Breastfeeding: History of breastfeeding and frequency and duration of current breastfeeding (i.e., exclusive breast feeding, % of mixed breast and formula feeding, exclusive formula feeding), timing of introduction of solids, and other breastfeeding behaviors and beliefs will be assessed via the validated Infant Feeding Questionnaire.¹⁶⁹ Postpartum Urine

Pregnancy Test and Postpartum Diabetes Screening (using ADA diagnostic criteria¹⁶³) will occur at each postpartum assessment.

D.12.5. Measures of Adherence

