Specific Aim #1, 2, 3: Impact of a Lifestyle Intervention on GWG and postpartum weight loss; biomarkers of insulin resistance; postpartum biomarkers of CVD risk. The primary analysis will evaluate differences in the change from baseline in weight gain measures, glycemia and other biomarkers of insulin resistance and cardiovascular risk factors between the groups (an intent to treat analysis). Initial analyses will describe the correlation of factors and investigate simple transformations for normality. The primary analysis will be based on a mixed model with random subject effects, including a common mean at baseline for the intervention groups, a period effect, and an intervention by period interaction.¹⁷⁰ The intervention by period interaction is a measure of the intervention effect, and corresponds to the estimate of an intervention effect in an analysis of covariance. The mixed model analysis will enable inclusion of time varying covariates such as depression, breastfeeding behaviors, and sleep, which may vary between baseline and follow-up for subjects. Equivalence of the intervention groups will be assessed by comparing the distribution of the potential confounders between each group. We will investigate established risk factors for weight gain (e.g., parity) and glycemia as well as degree and treatment for abnormality on glucose tolerance testing during pregnancy (e.g., diet, oral hypoglycemic and/or insulin) as potential confounders or effect modifiers. Generally, we will consider a change in the parameter estimate for the exposure (at least 15%), relative to that observed when not controlling for the variable as reflective of confounding. Effect modification will be evaluated by inspection of stratum specific odds ratios as well as by evaluating the statistical significance of interaction terms via likelihood ratio tests. We will also model the relationship between measured levels of exercise, sedentary behavior, and diet with each outcome, while adjusting for possible confounders using mixed effect linear regression models. We will test hypotheses with 2-sided tests. Finally, we will compare adoption and maintenance of behavior change (i.e., exercise, diet) in the intervention group relative to the control group by adding a fixed treatment group effect.

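### D.16 does not confine covariates in the arm comparison to pre-randomisation variables, and does not label other adjusted arm models as secondary

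*Combined protocol and SAP*

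**What the plan says.** D.16 (Aims 1-3) calls the arm comparison intent to treat and bases it on a mixed model "including a common mean at baseline for the intervention groups, a period effect, and an intervention by period interaction". That sentence names no other covariate.

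The same paragraph goes on: "The mixed model analysis will enable inclusion of time varying covariates such as depression, breastfeeding behaviors, and sleep". It will also examine "degree and treatment for abnormality on glucose tolerance testing during pregnancy (e.g., diet, oral hypoglycemic and/or insulin) as potential confounders or effect modifiers". Its working rule is "we will consider a change in the parameter estimate for the exposure (at least 15%), relative to that observed when not controlling", with such a change taken as a sign of confounding.

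D.5 places randomisation early: "Immediately prior to randomization (~12 weeks GA), participants will be evaluated for study inclusion". D.12.4 opens "We will consider the following factors as covariates" and sets no limit on timing. Its list includes "other pregnancy complications (e.g., hypertensive disorders, preterm birth, infection, cesarean delivery, NICU admission, Apgar score", postpartum sleep and depression, and "History of breastfeeding and frequency and duration of current breastfeeding".

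For Aim 4, D.16 applies the Aim 1-3 methods to the arm comparison of offspring outcomes. After a sentence on gestational weight gain (GWG) and prenatal glycaemia as predictors, it refers to the covariate list and adds birthweight-for-gestational-age (BW/GA) z-score to models of offspring weight gain. Table 4 lists that z-score as an Aim 4 outcome.

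**The concern.** Randomisation at about 12 weeks removes systematic confounding of the arm effect. A variable that arises later and responds to arm is not a confounder of that effect. It may be a mediator, or it may share causes with the outcome. Adjusting for it changes what is estimated, and a change-in-estimate rule cannot tell these cases apart, since a mediator moves the estimate just as a confounder would.

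The intervention targets diet, activity and weight. Later glucose-tolerance status, its treatment and birth size could therefore plausibly differ by arm. The plan does not say whether a flagged variable enters the arm model or which estimate is then reported. At stake is whether the published arm effect is the intent-to-treat effect that D.16 promises or a partial effect chosen after looking at the data.

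**Working it through.** **1. The plan's own figures.** Inputs are from D.17 and Table 3: two-sided alpha 5%, power 80%, n=300 in two equal arms. The two-sample t calculation gives a detectable difference of 0.3245 SD.
- Glucose: 13.27 x 0.3245 = 4.31 mg/dL (stated 4.3).
- GWG: 7.00 x 0.3245 = 2.27 kg (stated 2.3).
- HbA1c percent change: 7.4 x 0.3245 = 2.40 (stated 2.4).

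D.17 also mentions covariates explaining 20% of the variation. That would multiply each figure by sqrt(0.8) = 0.894, giving 3.85 mg/dL for glucose and 2.03 kg for GWG. The tabulated values match the unadjusted contrast.

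**2. Timing.** Of the variables that D.16 and D.12.4 allow, cesarean delivery, NICU admission, Apgar score, postpartum sleep and depression, current breastfeeding and BW/GA z-score can only arise after randomisation. Glucose-tolerance status and treatment raise the issue only where the test follows randomisation. For GWG, only prenatal variables matter.

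**3. Size and direction of the distortion.** In SD units, let d be the shift in the covariate caused by arm and R-squared the within-arm outcome variance it explains, so the slope is g = sqrt(R-squared). Then

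adjusted effect = total effect - g x d.

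If either d or g is zero there is no distortion. The sign of the product gives the direction. For a true 4.3 mg/dL:
- a mediated share of 15% or 30% leaves 4.3 x 0.85 = 3.7 or 4.3 x 0.70 = 3.0;
- masking by the same shares gives 4.3 x 1.15 = 4.9 or 4.3 x 1.30 = 5.6.

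**4. Behaviour of the 15% rule (simulation).** There were 20,000 trials per setting, with 150 per arm, one covariate and one follow-up. Covariate C = d x arm + N(0,1). Outcome Y = (total - g x d) x arm + g x C + error, with error variance 1 - R-squared. C enters the reported model if it moves the estimate by at least 15%. The documents give neither d nor R-squared, so both are assumptions. A 15% share needs g x d = 0.15 x 0.3245 = 0.049.

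| Mediated share | R-squared | Arm shift d (SD) | Flagged by rule | Power under rule | Power if always adjusted |
|---|---|---|---|---|---|
| 15% | 5% | 0.22 | 48% | about 69% | 68% |
| 15% | 10% | 0.15 | 50% | 71% | 71% |
| 15% | 20% | 0.11 | 55% | 74% | 76% |
| 30% | 10% | 0.31 | 90% | 53% | 53% |
| 30% | 20% | 0.22 | about 85% | 58% | 59% |

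The unadjusted contrast keeps 80% throughout. A 30% share at R-squared 5% would need a shift of 0.44 SD, larger than the outcome effect of 0.32 SD, and is left out.

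**5. No true arm effect, but a covariate that shares a cause with the outcome is shifted by arm.** False-positive rate under the rule, R-squared 5% to 20%:
- d = 0.1 SD: about 5-7%
- d = 0.2 SD: about 7-13%
- d = 0.3 SD: about 9-25%

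The unadjusted rate is 5%. A 0.3 SD shift is large: for a binary variable with an assumed prevalence of 10%, it is 0.3 x sqrt(0.10 x 0.90) = 0.09, or 9 percentage points.

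**6. Chance imbalance only (d = 0).** With a true effect, the rule flags the covariate in 12-36% of trials. The mean estimate stays within 1.5% of the truth and power is 81-86%. With no effect, type I error is 4.2-5.0%. This is not a harm.

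**7. A large effect.** At the HbA1c difference of 7.1% cited in D.17, a 30% loss leaves 7.1 x 0.7 = 4.97%. The standardised difference is 4.97/(7.4 x sqrt(4/300)) = 5.8, so power stays above 99.9%, but the estimate is still too small.

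**The case against.** The strongest reply is that the primary analysis is already specified. The three-term model names no follow-up covariate, Table 3 was computed on the unadjusted contrast, and no section says that an adjusted estimate replaces it. The covariate sentences say what a mixed model can accommodate and what will be explored. The word *exposure* in the 15% rule may refer to measured exercise, sedentary behaviour and diet, which D.16 also models with adjustment and where such a rule belongs. The next sentence speaks of odds ratios, which do not fit a continuous change outcome. All of this stands, and it keeps the point conditional. It does not settle it: the rule comes before the behaviour models are introduced and shortly after a sentence on comparing the randomised groups, so the arm reading remains open.

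Some stronger readings are tempting but not supported:
- *The primary analysis is biased as written.* It is not. Adjustment in Aims 1-3 is allowed, not prescribed.
- *Aim 4 arm comparisons will be adjusted for BW/GA.* That sentence follows the one on GWG and glycaemia as predictors, so its reach is unclear. BW/GA also resembles a starting value for the growth from birth described in D.12.2.
- *Power falls to 66% or 50%.* Those figures combine a 15% or 30% loss with no variance explained, but a covariate that explains no variance cannot remove any effect.
- *The 15% rule does harm through chance imbalance.* Step 6 shows otherwise.

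**Conclusion.** The gap is real and should be closed, but it is a missing restriction and not a demonstrated bias. The distortion needs four things together: a post-randomisation variable is entered, it responds to arm, it relates to the outcome, and the resulting estimate is reported as the arm effect. The documents establish none of these for Aims 1-3, and they do not exclude them either. What makes this more than missing detail is that the stated rule tends to select such variables: about half of trials for a mediator carrying 15% of the effect, and about 85-90% for one carrying 30%.

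The power and false-positive figures illustrate scale. They rest on assumed arm shifts and R-squared values, one covariate, one follow-up visit, and entry of the flagged variable in the reported model. They do not reproduce the planned repeated-measures analysis.

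**What to change.** In D.16:
- State that the reported primary arm effect for Aims 1-4 comes from the existing three-term model (for offspring outcomes without a baseline, the arm contrast), adjusted only for variables measured before randomisation, such as the randomisation strata of age and BMI.
- State that the 15% rule does not select covariates for the arm effect and is kept for the models of measured exercise, sedentary behaviour and diet.
- Label as secondary (explanatory) any arm model adjusted for follow-up depression or sleep, current breastfeeding, delivery events, post-randomisation glucose-tolerance status or treatment, or BW/GA z-score.
- Under Aim 4, restrict the BW/GA adjustment to the GWG and glycaemia predictor models, or label it secondary for the arm contrast.

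In D.12.4, mark each covariate as measured before or after randomisation.

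The cost is a few sentences and one annotation of a list. No new data are needed, no sample size changes, and every adjusted analysis remains available under its own label.

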We calculated the smallest mean difference in change from baseline in the Lifestyle Intervention vs. the Health & Wellness Control arm which we could detect at 80% power using standard deviations based on our prior studies and the literature^{47, 177-180} using 2-sided tests with a significance level of alpha=5% (NCSS PASS 2008 software). For multiple regression models, we assumed that covariates accounted for 20% of the variation. Tables 3 and 4 show we have excellent power to detect even ‘small to medium’ mean differences, as defined by Cohen,¹⁸¹ ranging from ~0.30 to 0.35 SDs for a range of representative outcome measures. For example, we have 80% power to detect as small as a 2.4% difference (Table 3) in percent change in HbA1c between treatment arms. A comparable trial among Hispanics observed a 7.1% difference in percent change in HbA1c between treatment arms¹⁸² demonstrating that detecting this difference is well within the capability of the lifestyle intervention. For the categorical outcome of Compliance with IOM GWG guidelines, given our observation that 51% of overweight/obese Hispanic women exceeded guidelines in the study population, we have 80% power to detect a 30% reduction in risk or larger for exceeding IOM guidelines.

Table 3. Power Calculations Corresponding to Aim #1-3.	Projected sample size for analysis	SD for Change from Baseline	Smallest detectable mean difference in change from baseline between arms
Aim #1: GWG & Postpartum Weight Loss			
GWG (kg)	300	7.00	2.3
Postpartum weight loss	264	6.00	2.1
Physical activity (MET-hrs/wk>mod intensity)	300	2.89	0.9
Physical activity (minutes>mod intensity)	300	38.05	12.3
Total Caloric Intake (kcal/day)	300	64.90	22.4
Aim #2: Biomarkers of Insulin Resistance			
Glucose (mg/dl)	300	13.27	4.3
Insulin (pmol/l)	300	14.20	4.6
HbA _{1c}	300	0.26	0.1
HbA _{1c} (percent change)	300	7.4%	2.4%
Adiponectin (μg/ml)	300	3.40	1.1
Leptin (ng/ml)	300	5.50	1.8
HOMA	300	1.00	0.3
Aim #3: Postpartum Biomarkers of CVD Risk			
Total cholesterol (mg/dL)	264	38.38	13.3
Triglycerides (mg/dL)	264	83.06	28.7
HDL-cholesterol (mg/dL)	264	7.59	2.6
LDL-cholesterol (mg/dL)	264	33.83	11.7
Systolic blood pressure (mm Hg)	264	12.23	4.2
Diastolic blood pressure (mm Hg)	264	7.64	2.6
CRP (mg/dl)	264	4.50	1.5

Table 4. Power Calculations Corresponding to Aim #4.	Projected sample size for analysis	SD	Smallest detectable mean difference between arms
Aim #4: Offspring Outcomes at Delivery			
Cord glucose (mg/dl)	288	14	4.6

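### D.16 judges confounding of the randomised arm effect by a 15% change-in-estimate rule whose candidates include post-randomisation variables, and cites odds ratios its linear models do not produce

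*Combined protocol and SAP*

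**What the plan says.** All of this is in the combined protocol and SAP.

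- **Primary model (D.16, Aims 1–3).** "The primary analysis will be based on a mixed model with random subject effects, including a common mean at baseline for the intervention groups", plus period and intervention-by-period terms. The interaction is the intervention effect and "corresponds to the estimate of an intervention effect in an analysis of covariance". The model is linear and the outcomes it names are changes in continuous measures.
- **Confounder rule (D.16).** "Generally, we will consider a change in the parameter estimate for the exposure (at least 15%), relative to that observed when not controlling". A shift of that size is taken to indicate confounding. The variables to be examined include parity and "degree and treatment for abnormality on glucose tolerance testing during pregnancy". Depression, breastfeeding and sleep are named as time-varying covariates that the model can include.
- **Effect modification (D.16).** "Effect modification will be evaluated by inspection of stratum specific odds ratios as well as by evaluating the statistical significance of interaction terms", the latter by likelihood ratio tests.
- **Randomisation (D.5).** At about 12 weeks, in blocks of 4, stratified by age and pre-pregnancy BMI. D.16 does not say that these two factors enter the model, and it gives no fixed covariate list.
- **Power (D.17).** For multiple regression models, "we assumed that covariates accounted for 20% of the variation". For the categorical weight-gain outcome, with 51% of women exceeding the guidelines, "we have 80% power to detect a 30% reduction in risk or larger for exceeding IOM guidelines".

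**The concern.** Change-in-estimate screening belongs to observational work, where an exposed group may differ systematically from an unexposed one. Here the exposure is a randomised arm. A baseline covariate differs between arms only by chance, so the rule responds to chance imbalance divided by the size of the estimate. It admits many covariates when the estimate is near zero and few when the effect is real, which is when a prognostic covariate would add power.

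The second problem is potentially worse. A glucose tolerance result, and treatment for it, come after randomisation at about 12 weeks and may be changed by a diet and exercise programme. For such a variable, a large change in the arm estimate may be mediation. Adjusting for it would then take away part of the effect being estimated.

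Third, a linear mixed model gives mean differences. For a continuous outcome there is no stratum-specific odds ratio to inspect, so the plan names a subgroup measure that cannot be computed for weight gain, glucose, lipids and the other outcomes in Table 3.

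**Working it through.** **1. The plan's own figure.** Inputs from D.17 and Table 3: N = 300 (150 per arm), SD 7.00 kg, two-sided alpha 5%, power 80%.

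Detectable difference = (1.960 + 0.842) × SD × √(4/N) = 2.802 × 7.00 × 0.1155 = 2.26 kg (2.27 with the t distribution). The table prints 2.3.

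With covariates explaining 20%, multiply by √0.80: 2.03 kg. The printed value is therefore the unadjusted one. Other rows agree:

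| Row | N | Unadjusted | With 20% | Printed |
|---|---|---|---|---|
| Glucose (mg/dl) | 300 | 4.29 | 3.84 | 4.3 |
| Postpartum weight loss | 264 | 2.07 | 1.85 | 2.1 |
| LDL-cholesterol (mg/dL) | 264 | 11.67 | 10.44 | 11.7 |
| Birthweight (g) | 288 | 211 | 189 | 212 |

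Two rows match neither column exactly: caloric intake (22.4) lies above both (21.0 and 18.8), and CRP (1.5) lies between them, nearer the unadjusted 1.55 than 1.39. No row checked points to use of the 20%.

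**2. What the rule responds to.** For one baseline covariate X with adjusted slope γ, the unadjusted minus the adjusted estimate equals γ × (difference in mean X between arms). Take X as standardised and explaining 20% of variance:

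- γ = 7 × √0.20 = 3.13 kg per SD.
- The chance difference in mean X has standard error √(4/300) = 0.115, so the shift has SD 3.13 × 0.115 = 0.36 kg.
- At an estimate of 2.3 kg the threshold is 0.15 × 2.3 = 0.345 kg, exceeded with probability about 0.34.
- At an estimate of 0.5 kg the threshold is 0.075 kg, exceeded with probability about 0.84.

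The covariate is equally prognostic in both cases. Only the size of the estimate differs.

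**3. Cost in power.** Simulation: 300 women, 1:1, SD 7, independent baseline covariates jointly explaining 20%, each tested singly against the 15% threshold, those flagged entered together, 6,000 trials per setting.

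| Covariates | Kept, no effect | Kept at 2.3 kg | Power unadjusted | Power, 15% rule | Power, all pre-specified |
|---|---|---|---|---|---|
| 1 | 0.82 | 0.34 | 81.0% | 86.1% | 88.6% |
| 2 | 1.44 | 0.45 | 80.6% | 85.5% | 88.2% |
| 5 | 2.88 | 0.47 | 81.1% | 84.3% | 88.1% |

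Runs at 2.27 kg with 2, 5 or 10 covariates gave 78–80%, 82–84% and 86–88%. Letting the covariates explain 10% to 30% puts the gap between the rule and pre-specification at about 2 to 5 points. Type I error under the rule was 4.2–4.8% at 20%, and 3.7–5.1% over all settings from 10% to 30%.

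**4. Post-randomisation candidates.** If a share m of the effect passes through a variable, adjusting for it changes the estimate by m on average, so any m above 15% tends to trip the rule. Illustration with assumed values: total effect 2.27 kg, m = 30%, variable explaining 20% of within-arm variance. The expected change is 0.30 × 2.27 = 0.68 kg against a threshold of 0.15 × 2.27 = 0.34 kg. In simulation the rule kept the variable in about 85% of trials, the mean estimate fell to 1.6 kg, and power fell from about 80% to 58%. The documents give no value for m.

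**5. Odds ratios.** For exceeding the guidelines, 51% × 0.70 = 35.7%. The risk ratio is 0.70, but the odds ratio is (0.357/0.643) ÷ (0.51/0.49) = 0.53. With a risk ratio of 0.70 in two strata and assumed control risks of 40% and 62%, the odds ratios are 0.58 and 0.47.

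**The case against.** The strongest reply is that D.16 defines its primary model before it mentions the 15% rule, and never says that flagged variables enter that model or that unflagged ones are left out. The same section plans non-randomised models of measured exercise, sedentary behaviour and diet, where confounder screening is ordinary. This stands as a limit on the claim, and the size of the problem is therefore conditional. It does not remove the gap, because the rule is written for the exposure estimate in the arm comparison and no fixed list says what is adjusted for.

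A reader might infer that the power stated in D.17 is lost. The documents do not support that: the tables reproduce without any covariate gain, and even under the rule simulated power exceeds the unadjusted figure. The baseline outcome, where there is one, is already handled by the common-baseline model.

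A reader might also infer that subgroups will be misread. That is too strong. The same sentence adds likelihood ratio tests of interaction. In the example above, with an assumed 75 women per arm per stratum, the log odds ratios differ by 0.22 with a standard error of 0.48, and an interaction test would flag this about 7% of the time against a nominal 5%. A constant odds ratio would in turn imply unequal risk ratios, so neither scale is correct in itself.

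Nor are odds ratios useless throughout. D.12.3 lists categorical outcomes: guideline compliance in three categories, the percentage retaining a given weight, and change of BMI category. Odds ratios could apply to these, but D.16 names no model for them.

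**Conclusion.** The concern holds in a limited form. The 15% rule is a poor basis for adjusting a randomised comparison. If it governs adjustment, it makes the adjusted estimate data-dependent and costs about 2 to 5 power points against a fixed list, with type I error near 5%. Those figures assume independent baseline covariates, one to ten in number, one-pass selection, and no balancing by the randomisation strata.

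The more serious risk is adjustment for glucose tolerance results and treatment, which could remove part of a real effect. Its size is unknown because it depends on how much of the effect passes through them. I take these variables as post-randomisation from D.3 and D.5 (recruitment at about 10 weeks, randomisation at about 12). D.12.4 gives no test week, and one sentence under Recruitment and Informed Consent, which places recruitment at routine gestational diabetes screening, conflicts with D.3.

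The odds-ratio wording is a mismatch with the named models. Its harm is limited by the interaction tests, but it leaves the continuous outcomes without a defined subgroup effect measure.

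**What to change.** In D.16, for the arm comparison:

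1. Replace the 15% rule with a short fixed list of baseline covariates, entered whatever they do to the estimate: the stratification factors age and pre-pregnancy BMI, parity, and the baseline outcome where the common-baseline model does not already handle it.
2. Keep post-randomisation variables (glucose tolerance result and treatment, and depression, breastfeeding and sleep measured during follow-up) out of the primary model. Any analysis using them should be labelled secondary.
3. If the change-in-estimate rule is kept at all, confine it to the non-randomised exercise and diet models.
4. For continuous outcomes, report effect modification as stratum-specific mean differences with confidence intervals from the arm-by-factor interaction.
5. For exceeding the weight-gain guidelines, name a model and report the effect on the risk scale that D.17 uses. Modified Poisson regression for a risk ratio is one option; the choice of model is a preference. Name a model for the other categorical outcomes in D.12.3 too.

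The cost is a change of analysis wording and a few degrees of freedom. No new data or visits are needed.
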